7.8. Treatment after the End of the Study

7.8.1. Continued Access

LY900014 will not be made available after conclusion of the study to patients. Rapid-acting insulin analogs and regular human insulin are available in all countries for use as prandial insulin.

7.8.2. Special Treatment Considerations

After discontinuation of IP at the end of the treatment period or earlier, randomized patients should restart the prandial insulin used prior to study entry or transition to a rapid-acting insulin analog other than insulin lispro if the patient was not treated with insulin lispro prestudy. Patients may continue treatment with the basal insulin used during the study or return to their prestudy basal insulin at investigator discretion.

During this follow-up period, OAMs used during the study treatment period should be continued and other prestudy OAMs may be considered at investigator discretion as appropriate.

Investigators should provide patients with appropriate guidance for glucose monitoring and insulin dose adjustment throughout the follow-up period in order to maintain glycemic control.

8. Discontinuation Criteria

8.1. Discontinuation from Study Treatment

In the event that a patient is discontinued from the study treatment, the investigator should encourage the patient to remain in the study for continued safety monitoring.

Lilly recognizes the importance of complete data collection. This study includes elements to minimize missing data. Randomized patients who are discontinued from IP before study completion are encouraged to remain in the study for continued monitoring. For patients who remain in the study after early discontinuation of IP, both efficacy (except MMTT) and safety data will be collected at scheduled visits. MMTT assessment will NOT be performed for these patients. The difference between stopping IP and discontinuing the study will be explained to patients as part of the informed consent, and patients will be encouraged to continue in the study even if they stop study drug. In addition, study site investigators will be trained on the importance of complete data collection, with additional re-education of sites and patients as necessary.

8.1.1. *Permanent Discontinuation from Study Treatment*

Patients will be discontinued from the IP in the following circumstances:

- The investigator may decide that the patient should stop IP. If this decision is made because of an AE, SAE, or a clinically significant laboratory value, the study drug is discontinued for that patient and appropriate measures are to be taken. Lilly or its designee is to be alerted.
- The patient requests to discontinue IP.
- If the patient becomes pregnant.
- If an investigator, study site personnel performing assessments, or patient is unblinded, the patient must discontinue IP.
- If the patient, for any reason, requires treatment with another therapeutic regimen or therapeutic agent that has been demonstrated to be effective for treatment of the study indication. Discontinuation from IP should occur prior to introduction of the new agent.
- Use of prohibited concomitant medication (see [Table ITSE.8](#)).
- If the patient has not taken IP for more than 14 consecutive days.
- **Discontinuation due to a hepatic event or liver test abnormality.** Patients who are discontinued from investigational product due to a hepatic event or liver test abnormality should have additional hepatic safety data collected via CRF.

Discontinuation of the investigational product for abnormal liver tests **should be** considered by the investigator when a patient meets one of the following conditions after consultation with the Lilly designated medical monitor:

- alanine aminotransferase (ALT) or aspartate aminotransferase (AST) >8X upper limit of normal (ULN)
- ALT or AST >5X ULN for more than 2 weeks
- ALT or AST >3X ULN and total bilirubin level (TBL) >2X ULN or international normalized ratio (INR) >1.5
- ALT or AST >3X ULN with the appearance of fatigue, nausea, vomiting, right upper-quadrant pain or tenderness, fever, rash, and/or eosinophilia (>5%)
- alkaline phosphatase (ALP) >3X ULN
- ALP >2.5X ULN and TBL >2X ULN
- ALP >2.5X ULN with the appearance of fatigue, nausea, vomiting, right quadrant pain or tenderness, fever, rash, and/or eosinophilia (>5%)

Patients discontinuing from the investigational product prematurely for any reason should complete adverse event and other follow-up procedures per Section 2 (Schedule of Activities), Section 9.2 (Adverse Events), and Section 9.4 (Safety) of this protocol.

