9.2. Adverse Events

Investigators are responsible for monitoring the safety of patients who have entered this study and for alerting Lilly or its designee to any event that seems unusual, even if this event may be considered an unanticipated benefit to the patient.

The investigator is responsible for the appropriate medical care of patients during the study.

Investigators must document their review of each laboratory safety report.

The investigator remains responsible for following, through an appropriate health care option, AEs that are serious or otherwise medically important, considered related to the IP or the study, or that caused the patient to discontinue the IP before completing the study. The patient should be followed until the event resolves, stabilizes with appropriate diagnostic evaluation, or is reasonably explained. The frequency of follow-up evaluations of the AE is left to the discretion of the investigator.

Lack of drug effect is not an AE in clinical studies, because the purpose of the clinical study is to establish treatment effect.

After the ICF is signed, study site personnel will record via electronic data entry the occurrence and nature of each patient's preexisting conditions, including clinically significant signs and symptoms of the disease under treatment in the study. In addition, site personnel will record any change in the condition(s) and any new conditions as AEs. Investigators should record their assessment of the potential relatedness of each AE to protocol procedure and/or IP, via electronic data entry.

The investigator will interpret and document whether or not an AE has a reasonable possibility of being related to study treatment, study device, or a study procedure, taking into account the disease, concomitant treatment, or pathologies.

A "reasonable possibility" means that there is a cause and effect relationship between the IP, study device, and/or study procedure and the AE.

The investigator answers yes/no when making this assessment.

Planned surgeries and nonsurgical interventions should not be reported as AEs unless the underlying medical condition has worsened during the course of the study.

If a patient's IP is discontinued as a result of an AE, study site personnel must report this to Lilly or its designee via electronic data entry, clarifying, if possible, the circumstances leading to any dosage modifications or discontinuations of treatment.

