9.4.6.1. Hepatic Safety Monitoring

If a study patient experiences elevated ALT $\geq 3X$ ULN, ALP $\geq 2X$ ULN, or elevated TBL $\geq 2X$ ULN, liver testing (Appendix 4) should be repeated within 3 to 5 days including ALT, AST, ALP, TBL, direct bilirubin, gamma-glutamyl transferase, and creatine kinase to confirm the abnormality and to determine if it is increasing or decreasing. If the abnormality persists or worsens, clinical and laboratory monitoring should be initiated by the investigator and in consultation with the study medical monitor. Monitoring of ALT, AST, TBL, and ALP should continue until levels normalize or return to approximate baseline levels.

Hepatic Safety Data Collection

Additional safety data should be collected via the CRF if 1 or more of the following conditions occur:

- elevation of serum ALT to $\geq 5X$ ULN on 2 or more consecutive blood tests
- elevated serum TBL to $\geq 2X$ ULN (except for cases of known Gilbert's syndrome)
- elevation of serum ALP to $\geq 2X$ ULN on 2 or more consecutive blood tests

- patient discontinued from treatment due to a hepatic event or abnormality of liver tests
- hepatic event considered to be an SAE.

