Appendix 4. Hepatic Monitoring Tests for Treatment-Emergent Abnormality

Selected tests may be obtained in the event of a treatment-emergent hepatic abnormality and may be required in follow-up with patients in consultation with the Lilly, or its designee, clinical research physician.

Hepatic Monitoring Tests

Hepatic Hematology^a

Hemoglobin
 Hematocrit
 RBC
 WBC
 Neutrophils, segmented
 Lymphocytes
 Monocytes
 Eosinophils
 Basophils
 Platelets

Hepatic Chemistry^a

Total bilirubin
 Direct bilirubin
 Alkaline phosphatase
 ALT
 AST
 GGT
 CPK

Haptoglobin^a

Hepatic Coagulation^a

Prothrombin time
 Prothrombin time, INR

Hepatic Serologies^{a,b}

Hepatitis A antibody, total
 Hepatitis A antibody, IgM
 Hepatitis B surface antigen
 Hepatitis B surface antibody
 Hepatitis B core antibody
 Hepatitis C antibody
 Hepatitis E antibody, IgG
 Hepatitis E antibody, IgM

Anti-nuclear antibody^a

Anti-smooth muscle antibody (or anti-actin antibody)^a

Abbreviations: ALT = alanine aminotransferase; AST = aspartate aminotransferase; CPK = creatinine phosphokinase; GGT = gamma-glutamyl transferase; Ig = immunoglobulin; INR = international normalized ratio; RBC = red blood cells; WBC = white blood cells.

^a Assayed by Lilly-designated or local laboratory (if test results are required urgently to manage patient care).

^b Reflex/confirmation dependent on regulatory requirements and/or testing availability.

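### Section 9.4.6.1 gives AST no trigger for the repeat liver panel or for hepatic CRF collection, although 8.1.1 makes AST alone a ground for considering an IP stop

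*Protocol*

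**What the plan says.** **Considering an IP stop (Protocol 8.1.1).** Seven liver-test conditions are listed, to be weighed by the investigator after consulting the sponsor's medical monitor. AST stands beside ALT in four of them: >8X ULN; "ALT or AST >5X ULN for more than 2 weeks"; >3X with TBL >2X or INR >1.5; and >3X with symptoms or eosinophilia. The other three concern ALP.

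**Repeat testing (Protocol 9.4.6.1).** The rule opens: "If a study patient experiences elevated ALT $\geq 3X$ ULN, ALP $\geq 2X$ ULN, or elevated TBL $\geq 2X$ ULN, liver testing". The repeat is due within 3 to 5 days and includes AST and creatine kinase. If the abnormality persists or worsens, clinical and laboratory monitoring begins, and "Monitoring of ALT, AST, TBL, and ALP should continue until levels normalize or return to approximate baseline levels".

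**Hepatic CRF collection (Protocol 9.4.6.1).** The transaminase item reads "elevation of serum ALT to $\geq 5X$ ULN on 2 or more consecutive blood tests". The other laboratory items are for TBL and ALP. Two further routes do not depend on a laboratory threshold: "patient discontinued from treatment due to a hepatic event or abnormality of liver tests", and a hepatic SAE.

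**AST elsewhere.** Exclusion 24 applies the same 3X ULN limit to ALT and AST at screening. SAP 6.12.4.4.3 tabulates both at 3X, 5X and 10X ULN, and provides profiles and listings when either reaches 3X during treatment.

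**The concern.** AST is measured once the 9.4.6.1 process is running, but it cannot start that process. For ALT, the protocol directs a prompt repeat and then monitoring until the value settles. For AST at the same level, with ALT, ALP and TBL below their thresholds, it directs neither, although 8.1.1 treats that AST value as a possible reason to stop IP. No reason is given for the difference, and the entry criteria and the SAP do not make it.

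What is at stake is patient safety monitoring. A condition defined by duration needs at least two dated values, and for an isolated AST rise nothing in 9.4.6.1 asks for the second one. The non-inferiority analysis of HbA1c does not depend on this.

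**Working it through.** No formula or planned figure is involved. The check follows an isolated AST rise (ALT <3X, ALP <2X, TBL <2X ULN) through the rules.

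**Step 1: triggers in 9.4.6.1.** Repeat within 3 to 5 days: not started. Continued monitoring: not started, because it follows the repeat. Laboratory thresholds for CRF collection: 0 of 3 met. CRF collection through an IP stop or hepatic SAE: possible, but only after that event.

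**Step 2: the four AST conditions in 8.1.1.**

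| Condition | What it needs | Position for AST |
|---|---|---|
| >8X ULN | One value | Can be met; no directed confirmation |
| >5X ULN for more than 2 weeks | At least two dated values | No second value directed |
| >3X with TBL >2X or INR >1.5 | AST plus TBL or INR | TBL limb: TBL already triggers the repeat. INR limb: not triggered, but INR ("Prothrombin time, INR") is listed only in the Appendix 4 work-up, which also contains AST |
| >3X with symptoms or eosinophilia | One AST value plus the finding | Can be met; no directed confirmation |

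So 1 condition depends on a second value that is not directed, 2 lack only a confirmation, and 1 is largely covered (1 + 2 + 1 = 4).

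**Step 3: when the two-week condition can matter.** Planned safety chemistry after screening falls at Visit 8 and at Visit 18 or early discontinuation (Schedule of Activities; SAP Table 6.2).

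- *Visit 18 or early discontinuation.* Under Protocol 7.2.1.5 the last study prandial dose is taken at or just before this point. A repeat helps to follow the patient but cannot inform an IP stop.
- *Visit 8.* The first blinded dose comes with the next meal after the MMTT and randomization (Schedule of Activities, footnote c). For a patient who stays on IP, the next planned chemistry is at Week 26, far beyond a two-week window.
- *Unplanned tests during treatment.* These can reveal a rise, but a further sample is again discretionary.

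**Step 4: CRF collection.** Giving AST the same item as ALT would affect only rises of at least 5X on consecutive tests. AST from 3X to below 5X would stay outside it, as ALT does.

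**Step 5: number of extra repeats.** The documents give no rate of isolated AST ≥3X ULN. *Assume* 0.1% to 0.5% per sample, for illustration only:

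- Visit 8, at most 564 samples: 564 × 0.001 = 0.56; 564 × 0.005 = 2.82.
- Visit 18 or early discontinuation, at most 564 samples: the same.
- Together, 1,128 samples: 1,128 × 0.001 = 1.13; 1,128 × 0.005 = 5.64.

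Unplanned tests are not counted. These figures are for AST ≥3X. Isolated AST >5X is a subset, and nothing in the documents allows an estimate of it.

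**The case against.** The strongest reply is that an isolated AST rise already has cover. "Investigators must document their review of each laboratory safety report" (Protocol 9.2). The same section requires follow-up of serious or otherwise medically important adverse events until they resolve, stabilize or are explained. Section 9.4.5 makes a clinically significant laboratory finding that leads to a diagnosis reportable as an adverse event. Under 8.1.1 the investigator may stop IP for any clinically significant laboratory value without proving two weeks' duration, and the medical monitor is consulted on the listed conditions. Appendix 4 is not tied to particular analytes: "Selected tests may be obtained in the event of a treatment-emergent hepatic abnormality". The SAP reports AST elevations from planned and unplanned tests, with or without a hepatic CRF.

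All of this is correct, and it rules out a reading that a reader might infer: that the AST stop condition cannot work, or that patients with raised AST go unfollowed. The documents do not support that. What stands is narrower. None of these provisions sets an AST threshold, a time limit or a directed second sample, and the protocol did not leave ALT, ALP or TBL to the same discretion.

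It can also be said that a trigger for monitoring need not mirror a list of stop conditions, and that AST may rise for reasons outside the liver. Both points are fair. An ALT-led trigger is a defensible choice, but the protocol does not state it as one, and creatine kinase is already in the repeat panel to help identify such rises.

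**Conclusion.** The inconsistency is real and minor. Section 9.4.6.1 omits AST as a trigger for the repeat panel and as a laboratory threshold for CRF collection, while 8.1.1, exclusion 24 and SAP 6.12.4.4.3 set AST beside ALT. For the two-week condition, the practical gap is confined to a Visit 8 rise in a patient who then starts blinded IP, and to unplanned tests during treatment. It would be wrong to infer that every planned sample bears on an IP stop, since the end-of-treatment samples cannot.

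The textual finding rests on no assumption. The count of extra repeats rests wholly on the assumed 0.1% to 0.5%, and it does not describe AST >5X. Sample size, alpha and the primary analysis are untouched. This is an optional improvement of the lowest severity.

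**What to change.** In Protocol 9.4.6.1:

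- Change the ALT part of the repeat-test trigger to *ALT or AST ≥3X ULN*.
- For consistency, change the transaminase item for CRF collection to *ALT or AST ≥5X ULN on 2 or more consecutive blood tests*.

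The INR, symptom, >8X and ALP conditions in 8.1.1 can stay as they are.

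The cost is two small wording changes and a few extra repeat panels: about 1.1 to 5.6 from planned samples under the assumed rate, plus any from unplanned tests. Some of these will follow AST rises that do not come from the liver.

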8.1.2. Temporary Discontinuation from Study Treatment

During the study, patients who temporarily discontinue the IP may be able to resume IP based on the following scenario:

Patient has not taken IP for 14 consecutive days or less:

- If the treatment regimen restarts within 14 days of when the patient initially stopped taking IP, patient may continue in the study and begin treatment again with IP. During this time, nonstudy insulins may have been used. If the patient decides to continue in the study, no early termination procedures will be completed. Patients will continue study visits through the safety follow-up.

8.1.3. Discontinuation of Inadvertently Enrolled Patients

If the sponsor or investigator identify a patient who did not meet enrollment criteria and was inadvertently enrolled, then the patient should be discontinued from study treatment unless there are extenuating circumstances that make it medically necessary for the patient to continue on study treatment. If the investigator and the sponsor CRP agree it is medically appropriate to continue, the investigator must obtain documented approval from the sponsor CRP to allow the inadvertently enrolled patient to continue in the study with or without treatment with investigational product. Safety follow up is as outlined in Section 2 (Schedule of Activities), Section 9.2 (Adverse Events), and Section 9.4 (Safety) of the protocol.

8.2. Discontinuation from the Study

Some possible reasons that may lead to permanent discontinuation include:

- Enrollment in any other clinical trial involving an IP or enrollment in any other type of medical research judged not to be scientifically or medically compatible with this study
- Participation in the study needs to be stopped for medical, safety, regulatory, or other reasons consistent with applicable laws, regulations, and good clinical practice (GCP)
- The investigator decides that the patient should be discontinued from the study
- The patient requests to be discontinued from the study
- The patient discontinues insulin lispro or study-allowed basal insulin regimen for >14 consecutive days in the lead-in period.

Patients who discontinue the study early, but after randomization, will have early discontinuation procedures performed as shown in the Schedule of Activities (Section 2).

Patients who discontinue during the lead-in period will not need to fast, have laboratory samples drawn, or complete questionnaires, but will have all other early discontinuation procedures performed.

Patients discontinuing from the study prematurely for any reason should complete AE and other safety follow-up per Section 2 (Schedule of Activities), Section 9.2 (Adverse Events), and Section 9.4 (Safety) of this protocol.

8.3. Lost to Follow-Up

A patient will be considered lost to follow-up if he or she repeatedly fails to return for scheduled visits and is unable to be contacted by the study site. Site personnel are expected to make diligent attempts to contact patients who fail to return for a scheduled visit or were otherwise unable to be followed up by the site.

9. Study Assessments and Procedures

Section 2 lists the Schedule of Activities, with the study procedures and their timing (including tolerance limits for timing).

Appendix 2 lists the laboratory tests that will be performed for this study.

Unless otherwise stated in the subsections below, all samples collected for specified laboratory tests will be destroyed within 60 days of receipt of confirmed test results. Certain samples may be retained for a longer period, if necessary, to comply with applicable laws, regulations, or laboratory certification standards.

9.1. Efficacy Assessments

9.1.1. Primary Efficacy Assessments

The primary efficacy measure is the change from baseline to Week 26 in HbA1c.

9.1.2. Secondary Efficacy Assessments

The following secondary efficacy measures will be collected at the times shown in the Schedule of Activities (Section 2).

- Fasting and PPG collected during the MMTT
 - 1-hour and 2-hour PPG excursions: serum glucose measured 1 hour and 2 hours after the start of a meal minus fasting serum glucose
 - Incremental areas under the serum glucose concentration-time curve from 0 to 30 minutes, 0 to 1 hour, 0 to 2 hours, 0 to 3 hours, and 0 to 4 hours after a meal; maximum serum glucose after a meal
 - Glucose variability measured by the coefficient of variation and standard deviation (SD)
- 1,5-Anhydroglucitol (1,5-AG)
- SMBG 10-point profiles (fasting, 1-hour post morning meal, 2-hours post morning meal, pre midday meal, 1-hour post midday meal, 2-hours post midday meal, pre evening meal, 1-hour post evening meal, 2-hours post evening meal, and bedtime)
 - 1-hour and 2-hour PPG excursions
 - Within- and between-day glucose variability measured by the coefficient of variation and SD
- Proportion of patients with HbA1c $\leq 6.5\%$ and $< 7.0\%$
- Prandial, basal, and total insulin dose (units and units/kg), and prandial/total insulin ratio.

9.1.3. Appropriateness of Assessments

All efficacy and safety assessments included in this study are generally regarded as reliable and accurate with respect to diabetes.

9.1.4. Study Procedures

The following procedures will be performed at the times shown in the Schedule of Activities (Section 2).

9.1.4.1. Four-Point Self-Monitoring Blood Glucose

Patients should be encouraged to measure a minimum of 4 SMBG readings daily to facilitate dose titration (consists of fasting [pre morning meal], pre midday meal, pre evening meal, and pre bedtime), with additional readings as needed for glucose self-management. 4-point SMBG is required on three nonconsecutive days in the one week before each visit. Site personnel may request additional SMBG monitoring from patients and/or assess SMBG values at other times (such as postprandial SMBG measurements) to make clinical management decisions. Missing values in 4-point SMBG profiles will not be considered protocol deviations unless, in the opinion of the investigator, they are excessive and reflect noncompliance with the protocol.

9.1.4.2. Ten-Point Self-Monitoring Blood Glucose

Patients in both study arms should be instructed to perform 10-point SMBG profiles prior to 3 visits during the study (Visits 8, 15, and 18). Three 10-point profiles should be done during the 2 weeks prior to each visit. Each 10-point profile during this 2-week time interval should be completed over a 1-day period, preferably on 3 nonconsecutive days (weekdays and weekends), as per the Schedule of Activities (Section 2). The 10-point profile consists of 10 SMBG measurements on the same day at premeal, 1-hour, and 2-hours after the start of the morning, midday, and evening meals, and at bedtime. The 10-point SMBG profile is inclusive of the daily 4-point SMBG readings. Patients should be encouraged to eat a morning, midday, and evening meal on the days that the 10-point SMBG is monitored. Premeal measurements should be taken before the patient begins eating the meal. Patients may eat a snack and cover with bolus insulin if that is their usual practice. Missing values in 10-point SMBG profiles will not be considered protocol deviations unless, in the opinion of the investigator, they are excessive and reflect noncompliance with the protocol.

